5.9 Subject Replacement Strategy

During Part A, subjects who discontinue for any reason other than toxicity will be replaced.

During Part B, subjects will not be replaced.

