5.2.1 Dose Selection/Modification

5.2.1.1 Dose Selection

[figure not shown]
The rationale for selection of doses to be used in this trial is provided in Section [4.2.3 – Rationale for Dose Selection](#).

Details on the dose calculation, preparation and administration are provided in the Pharmacy Manual. Dose levels to be explored in Part A are shown below.

Dose Level	ADX11-001	MEDI4736
1	1×10^9 cfu (Q4wks)	3 mg/kg (Q2wks)
2	1×10^9 cfu (Q4wks)	10 mg/kg (Q2wks)
-1	1×10^9 cfu (Q4wks)	1 mg/kg (Q2wks)

Part A of the study is a Phase 1 3+3 design of ADXS11-001 and MEDI4736 combination therapy. MEDI4736 and ADXS11-001 will be administered in sequential cohorts of 3-6 subjects with a minimum of 48 hours between initial dosing for each of the first 3 subjects enrolled in the study. The first cohort will enroll a minimum of 3 subjects according to a standard 3+3 design shown schematically below.

Figure 1 3 + 3 Design Schematic

- Subjects in the first cohort will receive a dose of MEDI4736 at 3 mg/kg and ADXS11-001 1×10^9 cfu (Dose Level 1).

- If no DLTs are experienced, the next dose level of ADXS11-001 1×10^9 cfu + MEDI4736 at 10 mg/kg (Dose Level 2) will be explored.
- If 1 DLT is experienced, 3 additional subjects will be enrolled. If there is 1 DLT among 6 subjects, the next dose level will be explored.
- If ≥ 2 DLTs are observed in the first dose cohort, the starting dose of MEDI4736 will be de-escalated to 1 mg/kg and a dose de-escalation cohort will be enrolled (Dose Level -1).

All decisions regarding dose escalation or de-escalation will be guided by the 3+3 study design and will be made by the sponsor in consultation with investigators. The sponsor reserves the right to expand the number of subjects in each of the cohorts to better evaluate safety and tolerability, and to evaluate other doses.

The dose that will be utilized in Part B will be the highest maximal dose level evaluated in Part A that has an observed DLT rate of $<33\%$.

Dose escalation/de-escalation decisions for MEDI4736 will use pre-defined DLT criteria (Section 5.2.1.1 – Dose Limiting Toxicities). Subjects who complete the DLT period may dose-escalate to the RP2D if approved by the sponsor.

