5.2.1.2 Dose Limiting Toxicities

Dose-limiting toxicities will be evaluated during the Phase 1 combination dose-determination phase. All toxicities will be graded using NCI CTCAE v 4.03. The period for evaluating DLT will be from the first dose of investigational product through 28 days post initial dose for each subject. The occurrence of any of the following will be considered a DLT, if judged by the investigator to be possibly, probably or definitely related to combination therapy.

1. Any \geq Grade 4 irAE
2. Any \geq Grade 3 colitis
3. Any \geq Grade 3 non-infectious pneumonitis irrespective of duration

4. Any Grade 3 irAE, excluding colitis or pneumonitis, that does not downgrade to Grade 2 within 3 days after onset of the event despite optimal medical management including systemic corticosteroids or does not downgrade to \leq Grade 1 or baseline within 14 days of AE onset
5. Liver transaminase elevation $\geq 5x$ but $\leq 8x$ ULN that does not downgrade to Grade 2 within 5 days after onset with optimal medical management, including systemic corticosteroids. Transaminase elevation $>8x$ ULN or total bilirubin $>5x$ ULN will be considered a DLT regardless of duration or reversibility.
6. Any increase in AST or ALT $>3x$ ULN and concurrent increase in total bilirubin $>2x$ ULN (Hy's Law).
7. Bacterial meningitis documented by symptoms and confirmed by lumbar puncture culture results
8. Listeremia: persistent (for 48-72 hours) symptoms consistent with listeremia (e.g., fever and muscle aches, often preceded by diarrhea or other gastrointestinal symptoms)
9. \geq Grade 3 flu-like symptoms or cytokine release syndrome symptoms that persist for >24 hours after study drug administration despite symptomatic treatment.
10. \geq Grade 2 allergic reaction (not due to antibiotic): will receive no further doses.
11. Any drug-related “non-irAE” \geq Grade 3 except for the exclusions listed below.
 - Grade 3 fatigue for ≤ 7 days
 - Grade 3 endocrine disorder (thyroid, pituitary, and/or adrenal insufficiency) that is managed with or without systemic corticosteroid therapy and/or hormone replacement therapy and the subject is asymptomatic.
 - Grade 3 inflammatory reaction attributed to a local antitumor response (e.g., inflammatory reaction at sites of metastatic disease, lymph nodes, etc.).

- Concurrent vitiligo or alopecia of any AE grade
- Grade 3 infusion-related reaction that resolves within 6 hours with appropriate clinical management.

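### The 5-day transaminase allowance in the DLT list never takes effect, and Section 5.9 lets a Part A subject stopped early for a non-DLT toxicity count as DLT-free

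*Combined protocol and SAP*

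**What the plan says.** **DLT list.** Section 5.2.1.2 opens with "The occurrence of any of the following will be considered a DLT", subject to at least possible relatedness, so items 1 to 11 are alternatives. Three of them bear on a transaminase rise:

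- Item 4 covers a Grade 3 immune-related event "that does not downgrade to Grade 2 within 3 days after onset of the event despite optimal medical management including systemic corticosteroids", or one that does not reach "Grade 1 or baseline within 14 days of AE onset". It exempts only colitis and pneumonitis.
- Item 5 covers a rise of 5 to 8 times ULN "that does not downgrade to Grade 2 within 5 days after onset with optimal medical management, including systemic corticosteroids". Above 8 times ULN the rise is a DLT whatever its duration.
- Item 11 covers drug-related events that are not immune-related, from "Grade 3 except for the exclusions listed below". Transaminases are not among those exclusions.

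**Window and decision.** "The period for evaluating DLT will be from the first dose of investigational product through 28 days post initial dose for each subject". Under Section 5.2.1.1, Part B uses the "highest maximal dose level evaluated in Part A that has an observed DLT rate of" less than 33%.

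**Replacement.** Section 5.9 gives one sentence for Part A: "During Part A, subjects who discontinue for any reason other than toxicity will be replaced". It mentions neither DLTs, doses received nor the 28-day window, and no DLT-evaluable set is defined elsewhere. Table 4 (Section 5.2.1.3) sets the toxicities for which combination treatment must stop.

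**The concern.** Part A has 6 to 18 subjects and a 3+3 rule, so how a single subject is classified can decide a dose level. The two gaps act in opposite directions.

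- **DLT list.** Item 5 reads as a deliberate tolerance for transaminase rises that settle within five days. If its neighbours cancel it, an event that the list was written to accept can stop escalation.
- **Replacement.** A rule based on the reason for stopping is harmless only if every toxicity stop is a DLT. If some are not, a subject who missed part of the planned exposure stays in the cohort with no DLT recorded, and a level can pass on fewer fully exposed subjects than 3+3 assumes.

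**Working it through.** **The plan's threshold.** 0/3 = 0% and 1/6 = 16.7% are below 33%; 1/3 and 2/6 = 33.3% are not. This agrees with the escalation bullets in Section 5.2.1.1: escalate on 0/3, or on 1/3 followed by no DLT in three more.

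**Transaminase items side by side.** Take a related rise above 5 and up to 8 times ULN. That this is Grade 3 is implied by item 5 itself and by the Grade 3 row of Table 4.

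| Day Grade 2 is reached | Item 5 alone | If immune-related (item 4) | If not (item 11) |
|---|---|---|---|
| 1–3 | not a DLT | not a DLT, if Grade 1 or baseline by day 14 | DLT |
| 4–5 | not a DLT | DLT | DLT |
| 6 or later | DLT | DLT | DLT |

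In every row where item 5 alone gives a DLT, item 4 or item 11 gives one too. In the day 4–5 row, where item 5 would spare the subject, one of the others does not. The 5-day allowance therefore changes no classification.

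*Size, given the event.* Suppose one of the first three subjects has such a rise, settling on day 4 or 5, and no other DLT. Let p be the true DLT rate in the other subjects (assumed, as the documents give none).

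- Counted as a DLT: escalation needs no DLT in the other five, (1−p)^5.
- Not counted: (1−p)^2 + 2p(1−p)(1−p)^3.

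| p | Not counted | Counted |
|---|---|---|
| 10% | 94.1% | 59.0% |
| 20% | 80.4% | 32.8% |
| 30% | 63.4% | 16.8% |

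**Toxicity stops that are not listed DLTs.** Comparing Table 4 with Section 5.2.1.2:

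- Grade 4 lymphopenia: excluded under item 11; Table 4 discontinues for Grade 4.
- A Grade 3 immune-related event in Table 4's residual category that resolves within item 4's limits: not a DLT; Table 4 discontinues.
- Grade 2 pneumonitis not resolved in 3 days: item 3 starts at Grade 3; Table 4 discontinues.

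The doses clearly inside the window are Week 1 ADXS11-001 and Week 1 and Week 3 MEDI4736 (Section 5.2.2.1). The stop costs one of these only if it comes before the Week 3 dose.

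*Size, given one such subject.* Let this subject carry a share f of the full-window DLT risk (assumed; f = 0 is the extreme).

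- In the first three: P = (1−p)^2(1−fp) + [2p(1−p)(1−fp) + (1−p)^2·fp](1−p)^3.
- At p = 0.3, f = 1: 0.343 + 0.441 × 0.343 = 0.494.
- At p = 0.3, f = 0: 0.490 + 0.420 × 0.343 = 0.634.

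| p | f = 1 | f = 0.5 | f = 0 |
|---|---|---|---|
| 10% | 90.6% | 92.4% | 94.1% |
| 20% | 70.9% | 75.6% | 80.4% |
| 30% | 49.4% | 56.4% | 63.4% |
| 40% | 30.9% | 38.7% | 46.4% |

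If the subject is instead among the second three, P = (1−p)^3 + 3p(1−p)^2·(1−p)^2(1−fp). At 30% this gives 49.4%, 52.7% and 55.9%.

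*Size on average.* If each subject independently has a chance q of being such a case, the per-subject DLT risk becomes p′ = p[1 − q(1−f)], and P = (1−p′)^3 + 3p′(1−p′)^5. At p = 0.3:

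- q = 2%, f = 0.5: p′ = 0.297, P = 50.0%, a rise of 0.6 points.
- q = 5%, f = 0: p′ = 0.285, P = 52.5%, a rise of 3.1 points.

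**The case against.** **On the transaminase item.** A dedicated rule is normally read as overriding general ones, and Table 4's own slower timetable for transaminases suggests that a tolerance was intended. That is a fair guess at intent, but no text says that item 5 prevails. Section 5.2.1.2 also calls for repeat laboratory testing before a laboratory finding is named a DLT, absent clinical abnormality. That confirms the value; it does not settle which time limit applies. The drop from 63.4% to 16.8% is simply what one counted DLT does in a 3+3 design and says nothing about frequency. A reader might infer that dose safety is compromised. It is not: the error over-counts DLTs.

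**On replacement.** The sponsor may expand cohorts (Section 5.2.1.1), an unlisted event may be designated a DLT (Section 5.2.1.2), and adverse events are followed for 30 days after stopping (Section 5.8). These reduce the harm. But the first two are optional, and follow-up restores observation, not exposure. Keeping toxicity stops in the cohort is also defensible, because removing them is informative exclusion. That part stands and shapes the fix.

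Three stronger readings go too far:

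- *A Grade 3 infusion reaction on Day 1 leaves a subject without ADXS11-001 and uncounted.* Item 10 already makes a Grade 2 or higher allergic reaction (not due to antibiotic) a DLT. The example survives only for a non-allergic Grade 3 reaction that resolves within 6 hours and is handled under Section 7.2.3.2 (no further infusions) rather than Table 5 (may continue after sponsor discussion).
- *The rule inflates escalation by 14 points.* That needs one such subject to have occurred in the first three, and f = 0, although the subject was dosed.
- *Any missed Week 3 dose should make a subject non-evaluable.* Table 4 holds treatment for ordinary Grade 2 events, so this would remove many subjects because of toxicity.

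**Conclusion.** The transaminase item is wrong as written. Item 5's 5-day allowance has no effect, and a related rise that settles on day 4 or 5 is a DLT on the literal text. The direction is conservative. The effect is large if such a rise occurs in a first cohort, but the documents give no rate for it.

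The replacement rule has a real but narrow gap, worth closing because closing it is cheap. At an assumed true DLT rate of 30%, one such subject in the first three raises the chance of escalating by 0 to 14.0 points, the top being an upper bound at f = 0. In the second three the rise is 0 to 6.5 points. Averaged over assumed case rates of 2–5% and f from 0 to 0.5, it is about 0.6 to 3 points. Section 5.9 is silent on the denominator, so the documents do not state that such subjects are counted as DLT-free; they only leave nothing that prevents it.

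**What to change.** **Section 5.2.1.2.** Exclude transaminase elevation from items 4 and 11 as 'governed by items 5 and 6'. Add to item 5: 'or does not downgrade to Grade 1 or less or baseline within 14 days of onset', so that item 4's longer limit is kept. Cost: slightly fewer DLTs counted. The limits at 14 days, above 8 times ULN and in item 6 still apply.

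**Section 5.9.** Add: 'A Part A subject who permanently stops treatment for a toxicity that is not a listed DLT before receiving the Week 1 ADXS11-001 dose and the Week 1 and Week 3 MEDI4736 doses is first reviewed for DLT designation under Section 5.2.1.2. If not designated a DLT, the subject is replaced and is not counted as DLT-free. A temporary hold or delay alone does not trigger replacement. Subjects who had a DLT or completed the 28-day window are not replaced.'

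Cost: an occasional replacement subject with a 28-day wait. Some toxicity stops also leave the denominator, which is why the DLT review comes first. Both changes are amendment wording.

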5.10 Clinical Criteria for Early Trial Termination

Early trial termination will be the result of the criteria specified below:

1. Quality or quantity of data recording is inaccurate or incomplete
2. Poor adherence to protocol and regulatory requirements
3. Incidence or severity of adverse drug reaction in this or other studies indicates a potential health hazard to subjects
4. Plans to modify or discontinue the development of the study drug

In the event of Sponsor decision to no longer supply study drug, ample notification will be provided so that appropriate adjustments to subject treatment can be made.

6.0 TRIAL FLOW CHART

6.1 Trial Flow Chart for Combination (Part A)

Trial Period:	Screening Phase		Treatment Period								End of Treatment				
	Treatment Cycle/Title:	Pre-screening	Screening	Wk 1	Wk 2	Wk 3	Wk 4	Wk 5	Wk 6	Wk 7	Wk 8	Discon	Follow-up Phone call	Follow up	Follow Up
Scheduling Window (Days):			-28 to -1	± 3 ¹		± 3		± 3		± 3		At time of Discon	30 days post	90 days post	Every 8 weeks post
Administrative Procedures															
Pre-screening Consent (H&N subjects only)		X													
HPV+ Test (H&N subjects only)		X													
Informed Consent			X												
Inclusion/Exclusion Criteria, Subject ID Card			X												
Demographics and Medical History			X												
Prior and Concomitant Medication Review			X	X		X		X		X					
MEDI4736 Administration (Q2wk)				X		X		X		X					
ADXS11-001 Administration (Q4wk) ²				X				X							
Clinical Procedures/Assessments															
Review Adverse Events				X		X		X		X		X	X	X	
Physical Examination ³			X	X		X		X		X		X			
Vital Signs and Weight ⁴			X	X		X		X		X		X			
ECOG Performance Status			X	X		X		X		X		X			
Tumor Imaging ⁵			X	X								X		X	
Laboratory Assessments⁶															
Pregnancy Test – Urine or Serum β-HCG			X	X		X		X		X					
PT/INR and aPTT			X	X		X		X		X		X			
CBC with Differential			X	X		X		X		X		X			
Comprehensive Serum Chemistry Panel			X	X		X		X		X		X			
Urinalysis			X	X		X		X		X		X			
T3, T4 and TSH			X	X		X		X		X		X			

Trial Period:	Screening Phase		Treatment Period								End of Treatment				
	Treatment Cycle/Title:	Pre-screening	Screening	Wk 1	Wk 2	Wk 3	Wk 4	Wk 5	Wk 6	Wk 7	Wk 8	Discon	Follow-up Phone call	Follow up	Follow Up
Scheduling Window (Days):		-28 to -1	$\pm 3^1$			± 3		± 3		± 3		At time of Discon	30 days post	90 days post	Every 8 weeks post
Tissue/Blood Collection															
PK Assessment ⁹				X		X		X		X		X		X	
Immunogenicity (ADA) Assessment (serum) ¹⁰				X				X		X		X		X	

1 - The +/- 3 day window does not apply to Cycle 1, Week 1. This window is applicable in all subsequent cycles.

2 - Subjects will receive prophylactic NSAIDS and antiemetics [REDACTED] before each ADXS11-001 infusion. Subjects will also receive a course of oral antibiotics to be started 3 days after each ADXS11-001 infusion.

3 - ECG and O₂ saturation by pulse oximetry at baseline screening only

4 - Vital signs are to be monitored [REDACTED] following each ADXS11-001 infusion.

5 - Tumor Assessments will be done in screening and Week 1 (± 1 week), starting at Cycle 2. Evaluations will continue every 8 weeks (± 1 week) during treatment and for subjects in follow up who discontinue treatment for reasons other than disease progression; duration of follow up will be up to 3 years.

6 - Screening lab that are done within 5 days of initiating treatment can be used for C1D1 laboratory tests.

7 - [REDACTED]

8 - [REDACTED]

9 - PK Assessment: Serum will be collected at Cycle 1 Day 1 (pre-dose and end of infusion), at Weeks 3 and 5 (pre-dose only) and at Week 7 (pre-dose and end of infusion). For all subsequent cycles, serum will be collected at Week 7 (pre-dose only) with the exception of Cycle 3 where serum will be collected at Week 7 (pre-dose and end of infusion). Serum will also be collected at end of treatment and at the 90-day post treatment follow up visit.

10 - Immunogenicity (ADA) Assessment: Serum will be collected at Cycle 1 Day 1 (pre-dose only), at Weeks 5 and 7 (pre-dose only). For all subsequent cycles, serum will be collected at Week 7 (pre-dose only). Serum will also be collected at end of treatment and at the 90-day post treatment follow up visit.

11 [REDACTED]

12 [REDACTED]

6.2 Trial Flow Chart for ADXS11-001 Monotherapy (Part B)

Trial Period:	Screening Phase		Treatment Period								Follow up		
Treatment Cycle/Title:	Pre-screening	Screening	Wk 1	Wk 2	Wk 3	Wk 4	Wk 5	Wk 6	Wk 7	Wk 8	Discon	Follow-up Phone Call ²	Follow Up
Scheduling Window (Days):		-28 to -1	$\pm 3^1$				± 3				At time of Discon	30/90 days post discon	Every 8 weeks post discon
Administrative Procedures													
Pre-screening Consent (H&N Subjects only)	X												
HPV+ Test (H&N subjects only)	X												
Informed Consent		X											
Inclusion/Exclusion Criteria		X											
Subject Identification Card		X											
Demographics and Medical History		X											
Prior and Concomitant Medication Review		X	X				X						
ADXS11-001 Administration (Q4wk) ³			X				X						
Clinical Procedures/Assessments													
Review Adverse Events			X				X				X	X	
Physical Examination ⁴		X	X				X				X		
Vital Signs and Weight ⁵		X	X				X				X		
ECOG Performance Status		X	X				X				X		
Tumor Imaging ⁶			X	X							X		X
Laboratory Assessments⁷													
Pregnancy Test – Urine or Serum β -HCG		X	X				X						
PT/INR and aPTT		X	X				X				X		
CBC with Differential		X	X				X				X		
Comprehensive Serum Chemistry Panel		X	X				X				X		
Urinalysis		X	X				X				X		

Trial Period:	Screening Phase		Treatment Period								Follow up		
	Pre-screening	Screening	Wk 1	Wk 2	Wk 3	Wk 4	Wk 5	Wk 6	Wk 7	Wk 8	Discon	Follow-up Phone Call ²	Follow Up
Treatment Cycle/Title:													
Scheduling Window (Days):		-28 to -1	$\pm 3^1$				± 3				At time of Discon	30/90 days post discon	Every 8 weeks post discon

Tissue/Blood Collection

1 - The +/- 3 day window does not apply to Cycle 1, Week 1. This window is only applicable in all subsequent cycles.

2 - Safety Follow up will be conducted via telephone. Safety Follow up at 30 days (± 1 week) for AEs and at 90 days (± 1 week) for SAEs.

3 - Subjects will receive prophylactic NSAIDS and antiemetics [REDACTED] before each ADXS11-001 infusion. Subjects will also receive a course of oral antibiotics to be started 3 days after each ADXS11-001 infusion

4 - ECG and O₂ saturation by pulse oximetry at baseline screening only

5 - Vital signs are to be monitored [REDACTED] following each ADXS11-001 infusion.

6 - Tumor Assessments will be done in screening and Week 1 (± 1 week), starting at Cycle 2. Evaluations will continue every 8 weeks (± 1 week) during treatment and for subjects in follow up who discontinue treatment for reasons other than disease progression; duration of follow up will be up to 3 years.

7 - Screening lab that are done within 5 days of initiating treatment can be used for C1D1 laboratory tests.

8 - [REDACTED]

9 - [REDACTED]

10 - [REDACTED]

11 - [REDACTED]

6.3 Trial Flow Chart for MEDI4736 Monotherapy arm (Part B)

Trial Period:	Screening Phase		Treatment Period								End of Treatment			
	Treatment Cycle/Title:	Pre-screening	Screening	Wk 1	Wk 2	Wk 3	Wk 4	Wk 5	Wk 6	Wk 7	Wk 8	Discon	Follow-up Phone Call	Follow up
Scheduling Window (Days):		-28 to -1	± 3 ¹		± 3		± 3		± 3		At time of Discon	30 days post	90 days post	Every 8 weeks post
Administrative Procedures														
Pre-screening Consent (H&N subjects only)	X													
HPV+ Test (H&N subjects only)	X													
Informed Consent		X												
Inclusion/Exclusion Criteria		X												
Subject Identification Card		X												
Demographics and Medical History		X												
Prior and Concomitant Medication Review		X	X		X		X		X					
MEDI4736 Administration (Q2wk)			X		X		X		X					
Clinical Procedures/Assessments														
Review Adverse Events			X		X		X		X		X	X	X	
Physical Examination ²			X	X		X		X		X		X		
Vital Signs and Weight			X	X		X		X		X		X		
ECOG Performance Status			X	X		X		X		X		X		
Tumor Imaging ³			X	X							X			X
Laboratory Assessments⁴														
Pregnancy Test – Urine or Serum β-HCG			X	X		X		X		X				
PT/INR and aPTT			X	X		X		X		X		X		
CBC with Differential			X	X		X		X		X		X		
Comprehensive Serum Chemistry Panel ⁵			X	X		X		X		X		X		
Urinalysis			X	X		X		X		X		X		
T3, T4 and TSH			X	X		X		X		X		X		
Tissue/Blood Collection														

Trial Period:	Screening Phase		Treatment Period								End of Treatment			
	Pre-screening	Screening	Wk 1	Wk 2	Wk 3	Wk 4	Wk 5	Wk 6	Wk 7	Wk 8	Discon	Follow-up Phone Call	Follow up	Follow Up
Treatment Cycle/Title:														
Scheduling Window (Days):		-28 to -1	$\pm 3^1$		± 3		± 3		± 3		At time of Discon	30 days post	90 days post	Every 8 weeks post
PK Assessment ⁷			X		X		X		X		X		X	
Immunogenicity (ADA) Assessment (serum) ⁸			X			X		X		X		X		

1 – The \pm 3 day window does not apply to Cycle 1 Week 1. This window is only applicable in subsequent cycles.

2 - ECG and O2 saturation by pulse oximetry at baseline screening only

3 - Tumor Assessments will be done in screening and Week 1 (\pm 1 week), starting at Cycle 2. Evaluations will continue every 8 weeks (\pm 1 week) during treatment and for subjects in follow up who discontinue treatment for reasons other than disease progression; duration of follow up will be up to 3 years.

4 - Screening lab that are done within 5 days of initiating treatment can be used for C1D1 laboratory tests.

5 -

6 - ()

7 - PK Assessment: Serum will be collected at Cycle 1 Day 1 (pre-dose and end of infusion), at Weeks 3 and 5 (pre-dose only) and at Week 7 (pre-dose and end of infusion). For all subsequent cycles, serum will be collected at Week 7 (pre-dose only) with the exception of Cycle 3 where serum will be collected at Week 7 (pre-dose and end of infusion). Serum will also be collected at end of treatment and at the 90-day post treatment follow up visit.

8 - Immunogenicity (ADA) Assessment: Serum will be collected at Cycle 1 Day 1 (pre-dose only), at Weeks 5 and 7 (pre-dose only). For all subsequent cycles, serum will be collected at Week 7 (pre-dose only). Serum will also be collected at end of treatment and at the 90-day post treatment follow up visit.

9 -

10 -

